- To assess efficacy of a single i.v. dose of MCS110 in reducing the size of PVNS tumors over 4 weeks evaluated by volume of PVNS lesion by MRI.
- To assess safety and tolerability of MCS110 in this population.

Part B/C

- To assess efficacy of multiple doses of MCS110 in reducing the size of PVNS or GCTTS tumors 8 weeks following the last dose evaluated by volume of PVNS or GCTTS lesion by MRI.
- To assess safety and tolerability of MCS110 in this population.

Key secondary objectives:

Part A and Part B and C

• To characterize the PK of single (Part A) and multiple doses (Part B) of MCS110 in PVNS or GCTTS (GCTTS only in Part B) patients.

Confidential

- To assess total M-CSF circulating levels in PVNS or GCTTS (GCTTS only in Part B and C) patients.
- To assess the mode of action of MCS110 by measuring serum C-terminal Type I Collagen peptide (CTX-I), a biomarker of bone resorption.
- To assess the immunogenicity of MCS110 in this population.
- To assess the duration of clinical response, if any, by joint range of motion.
- To assess the degree of functional recovery using questionnaires.

Part B/C

- To assess joint pain using a visual analog scale (VAS).
- To assess time to surgery.
- To assess time to relapse (based on MRI).

Study design Part A:

A randomized, double-blind, placebo controlled study with 2 arms; MCS110 or placebo.

Study design Part B:

A randomized, double-blind, placebo controlled study with 2 arms; MCS110 or placebo followed by MCS110 single arm, open label part.

Study design Part C:

A randomized, double-blind study with 3 parallel arms (3 mg/kg, 5 mg/kg, and 10 mg/kg of MCS110).

Population Part A:

The study population will be comprised of males and females aged 18 years or older with diagnosis of PVNS, who had no more than two surgeries. A total of up to 12 patients will be enrolled to participate in the study.

Population Part B:

The study population will be comprised of males and females aged 18 years or older with diagnosis of PVNS or GCTTS with an evaluable tumor size by MRI.

Population Part C:

The study population will be comprised of males and females aged 12 years or older with diagnosis of PVNS or GCTTS with an evaluable tumor size by MRI.

Inclusion/Exclusion criteria:

For full inclusion / exclusion please see Section 4.

Key Inclusion:

Part A

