 Men and women aged ≥ 18 years with diagnosis of PVNS, who have at least one measurable site of disease on MRI and are expected to undergo surgery, will be eligible to participate in the study.

Part B

• Men and women aged ≥ 18 years with diagnosis of PVNS or GCTTS, who have at least one measurable site of disease on MRI, will be eligible to participate in the study.

Confidential

Part C

Men and women aged ≥ 12 years with diagnosis of PVNS or GCTTS, who have at least one measurable site of disease on MRI, will be eligible to participate in the study.
 Adolescents (≥ 12, <18 years old) eligible for enrollment need to have (1) symptomatic disease for which surgical intervention is indicated and the surgical procedure itself would be associated with significant morbidity, or (2) recurrent disease.

Key Exclusions:

Part A

 Patients with PVNS, who have had more than two operations on the affected joint (not including diagnostic biopsies) or have received chemotherapy or radiation therapy to treat PVNS.
 Previous operations to a different joint from the one now being treated are not exclusionary.

Part B and Part C

 Patients with PVNS or GCTTS whose tumor is not evaluable by MRI, in the judgment of the central MRI reading site.

Parts A, B and C

- Patients who have undergone major surgery ≤ three (3) months prior to starting study drug or who have not recovered from side effects of such therapy. Any systemic illness that precludes definitive surgery for PVNS, or increases the risk to patients due to potential immunosuppression.
- Use of any intra-articularly administered drug (to the joint affected by PVNS) within 4 weeks prior to dosing.
- Patients with elevated troponin T and creatinine kinase (CK) levels (> 1.5 x ULN for the laboratory) at the screening and/ or baseline.
- Patients with dermal change indicative of lymphedema, or phlebolymphedema; specifically, any trace thickening, faint discoloration, swelling or obscuration of anatomic architecture on close inspection suggesting edema. In addition there must be no pitting edema at any site, particularly the head (periorbital), neck, trunk, genital and visceral areas.
- Patients, who are currently receiving immunosuppressive treatment, including systemic corticosteroids greater than the equivalent of 10 mg of prednisone, which cannot be discontinued at least 4 weeks prior to starting study drug.
- Patients engaged in or planning to enter a resistance exercise training program.

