patients with a history of renal diseases are excluded. Serum creatinine will be monitored to follow kidney function. Alveolar macrophages may be affected as well – although this was not observed in preclinical toxicology studies - and consequently patients with a history of lung disease are excluded from recruitment. Furthermore, monocyte derived cells are found as microglial cells in the brain as well as within the bone marrow, spleen, lymph nodes, skin and serosal surfaces. Patients will be closely monitored with physical examination to detect changes.

 Risks associated with MCS110 induced reduction in osteoclasts are hypocalcemia and hypophosphatemia and changes in bone turnover/homeostasis: Corporate Confidential Information

Patients who are enrolled in this study must have normal serum ionized calcium and serum phosphate at screening and baseline and will be closely monitored for the calcium levels at regular intervals throughout the study. Patients who develop hypocalcemia or hypophosphatemia will receive immediate treatment and will be monitored at least on a weekly basis until they return to the normal range. Changes in bone turnover and bone homeostasis will be closely monitored. Corporate Confidential Information

• Risk of developing swelling:

Corporate Confidential Information

Two subjects in the highest dose group used in this study did develop non-pitting periorbital swelling; however, the overall conclusion of the abstract was that the therapy was tolerated well suggesting that Pfizer observed reversibility Periorbital swelling was observed in 1 of 5 patients in Part A, in 6 of 11 MCS110 treated patients in part B and in 15/18 patients in Part C. In all patients, periorbital swelling was mild and did not require any treatment. Periorbital swelling generally lasted between 6 and 30 days, however in one patient it was reported 2 times. The first time it lasted only a few days and the second time it lasted for almost 4 months. We will exclude patients with an increased risk in developing edema, such as those with renal, hepatic, or cardiac dysfunction. Furthermore, the development of swelling will be followed throughout the study by regular physical examination and serial body weight measurements.

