3.5.5 Risk/benefit assessment

Corporate Confidential Information

Any potential immunosuppressive risks of MCS110 should be self-limited after the dose is cleared. Potential development of periorbital edema and rash, which was observed frequently with multiple doses of 10 mg/kg MCS110 is expected to be mild and reversible and not expected to occur with the lower doses tested. Patients will only be re-dosed once the AE resolved. If lower dose is not efficacious, patients will receive 3 doses of 10 mg/kg MCS110 to allow for tumor volume reduction. Based on the known effects of antiresorptive agents on bone in children, it is likely that MCS110 can be administered without serious consequences to an adolescent population for a limited amount of time such as 6 months, and that the effects should be fully reversible after withdrawal of the compound.

Adherence to the inclusion and exclusion criteria and close clinical monitoring are considered sufficient to minimize the potential risks to the patients.

Corporate Confidential Information

Corporate Confidential Information

4 Population

The study population will be comprised of males and females aged 18 (in Part C \geq 12) or older and diagnosed with PVNS (Part A) or GCTTS (giant cell tumor of the tendon sheath). Up to 18 evaluable patients were recruited in total in Parts A and B and approximately 19 patients will be recruited in Part C (approx. 15 in double blind phase and if a new efficacious dose is determined, 4 additional patients will be recruited in this arm in open label), where "evaluable" patient is defined as completing the protocol through follow-up MRI (approximately day 28 for Part A and earliest after second dose for Part B and after the third dose for Part C); patients who are dosed but are not evaluable will be replaced at the discretion of the sponsor. Part A recruitment will continue until amended protocol Part B is approved by IRB. Part B patients will continue in follow-up in parallel of Part C patients. The investigator must ensure that all patients being considered for the study meet the following eligibility criteria. No additional exclusions should be applied by the investigator, in order that the study population will be representative of all eligible patients.

Patient selection is to be established by checking through all inclusion/exclusion criteria at screening and study baseline. A relevant record (e.g., checklist) must be stored with the source documentation at the study site.

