4.2.4 Parts A, Part B and Part C

Patients fulfilling **any** of the following criteria are not eligible for inclusion in this study:

- 1. Use of other investigational drugs at the time of enrollment, or within 30 days or 5 half-lives of enrollment, whichever is longer; or longer if required by local regulations, and for any other limitation of participation in an investigational trial based on local regulations.
- 2. A known hypersensitivity to the study drug or drugs similar to the study drug. Patients who ever experienced a cytokine release syndrome/acute infusion reaction in response to treatment with an agent (e.g., monoclonal antibodies or other biological agents) are also excluded.
- 3. Patients who have undergone major surgery \leq three (3) months prior to starting study drug or who have not recovered from side effects of such therapy.

- 4. Patients with a history of coagulation disorders (hemorrhage or thrombosis).
- 5. Any systemic illness that increases the risk to patients due to potential immunosuppression:
 - a. Congestive heart failure, cancer (with the exception of excised superficial lesions such as basal cell carcinoma and squamous cell carcinoma of the skin), uncontrolled diabetes mellitus (fasted glucose > 180 mg/dL,), rheumatoid arthritis, systemic lupus erythematosus, inflammatory bowel disease, or other chronic inflammatory disease.
 - b. History or serological evidence of HIV infection, hepatitis B or C infection (positive Hepatitis B surface antigen (HBsAg) or Hepatitis C test result in adults).
 - c. History or serological evidence of active or latent tuberculosis (TB) as indicated by a positive QuantiFERON (in adults) or PPD skin test (in adolescents) at screening.
 - d. History of systemic fungal infection (e.g., histoplasmosis, coccidiomycosis, etc.) or systemic bacterial infection requiring parenteral antibiotic therapy within the past two years.
 - e. Evidence of any unresolved infectious illness within the past 2 weeks.
- 6. Pregnant or nursing (lactating) women.
- 7. Use of any intraarticularly administered drug (to the joint affected by PVNS) within 4 weeks prior to dosing.

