- For patients ≥18 years old: Donation or loss of 400 mL or more of blood within eight (8) weeks prior to initial dosing, or longer if required by local regulation. For patients ≥12 <18 years old: loss of ≥ 10% of blood within eight (8) weeks prior to screening, or longer if required by local regulation. The total blood volume of a child should be calculated based on the WHO recommendation (Howie 2011).
- 9. Hemoglobin level below 11.5 g/dL at screening.
- 10. Recent (within the last three [3] years) and/or recurrent history of acute or chronic bronchospastic disease (including asthma and chronic obstructive pulmonary disease, treated or not treated), or history of atopic allergy (asthma, urticaria, eczematous dermatitis).
- 11. Evidence of liver disease or liver injury as indicated by abnormal liver function tests such as SGOT (AST), SGPT (ALT), γ-GT, alkaline phosphatase, or serum bilirubin.
 - a. Any *single parameter* may not exceed 2 x upper limit of normal (ULN). A single parameter elevated up to and including 2 x ULN should be re-checked once more *as soon as possible*, and in all cases, at least prior to enrollment/randomization, to rule out lab error.
 - b. Any elevation of more than one parameter excludes a patient from participation in the study. Testing may be repeated once more as soon as possible, but in all cases, at least prior to enrollment/randomization, to rule out lab error.

Re-check results must be within normal limits in order for patient to qualify.

- 12. History or presence of impaired renal function as indicated by clinically significantly abnormal creatinine or BUN and/or urea values, or abnormal urinary constituents (e.g., albuminuria).
- 13. Patients with elevated troponin T and/or CK levels (> 1.5 x ULN for the laboratory) or with history of myositis, rhabdomyolysis or other myopathic disease.

- 14. Concomitant disease(s) known to influence calcium metabolism of bone, including hyperparathyroidism, hyperthyroidism, Paget's disease, osteogenesis imperfecta, and/or osteomalacia.
- 15. Patients with dermal change indicative of lymphedema, or phlebolymphedema; specifically, any trace thickening, faint discoloration, swelling or obscuration of anatomic architecture on close inspection suggesting edema and no pitting edema at any site, particularly head (periorbital), neck, trunk, genital and visceral areas.

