If a patient develops periorbitalswelling, subsequent dosing (e.g., 4 wks, 8 wks) will be put on hold until one week after the swelling has resolved.

If a patient develops any adverse event considered as drug related by the investigator, which has not resolved before the following dose, next dosing will be delayed until considered resolved.

If there are abnormal hematology and / or biochemistry laboratory values (CTCAE grade 3) judged as clinically significant by the Investigator, the next dose will be delayed until abnormalities have resolved. Isolated CK increase with normal troponin T and aldolase is not considered a safety concern even if reaching CTCAE grade 3.

Part B: If dosing of 4 times 10 mg/kg MCS110 (once every 4 weeks) is exceeding the initial 13 weeks dosing period, (due to occurrence of AEs) further dosing will be allowed up to week 20 if all AEs had resolved for more than a week and efficacy assessment demonstrates response to treatment (>50 % of tumor volume reduction after 3^{rd} dose in Part B, 45% in Part C) of these patients.

Dosing extension to 6 consecutive doses once every 4 weeks

Patients initially receive 4 consecutive doses once every 4 weeks (week 0, 4, 8, 12). Patients will receive 1 or 2 additional doses under the following conditions:

- no treatment related safety issues (for periorbital swelling* only if >grade 2) resulting in dosing delay during the first 4 doses the tumor has not been completely eliminated after the 3rd dose [determined by MRI at week 12]
- the tumor did respond to treatment (Part B: >50 % tumor volume reduction) after the 3rd dose [determined by MRI at week 12] Corporate Confidential Information

In Part C additional criteria apply as following:

- Part C (arms 3 mg/kg or 5 mg/kg): the tumor did respond to treatment (≥45 % tumor volume reduction) after the 3rd dose [determined by MRI at week 12] and MCS110 was tolerated: the patient will receive 3 additional doses of the same as dose level
- Part C (arms 3 mg/kg or 5 mg/kg): the tumor response to treatment is <45 % of tumor volume reduction after the 3rd dose [determined by MRI at week 12] and MCS110 was tolerated: the patient will receive doses increased to 10 mg/kg
- Part C (arm 10 mg/kg): the tumor did respond to treatment (≥45 % tumor volume reduction) after the 3rd dose [determined by MRI at week 12] and MCS110 was tolerated: the patient will receive 3 additional doses of 10 mg/kg

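### Exclusion criterion 15 makes absence of pitting edema part of the reason to exclude, so pitting edema does not itself exclude a patient as the synopsis requires

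*Protocol*

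**What the plan says.** The exclusion list in Protocol section 4.2.4 opens with the rule "Patients fulfilling any of the following criteria are not eligible for inclusion in this study". Criterion 15 in that list concerns skin changes that point to lymphedema or phlebolymphedema. It names the signs to look for, swelling among them, and ends "suggesting edema and no pitting edema at any site, particularly head (periorbital), neck, trunk, genital and visceral areas".

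The synopsis, under Key Exclusions for Parts A, B and C, gives the same skin signs and then closes the sentence. A new sentence follows: "In addition there must be no pitting edema at any site, particularly the head (periorbital), neck, trunk, genital and visceral areas".

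The synopsis presents its list as a selection and defers to the body of the protocol: "For full inclusion / exclusion please see Section 4". Section 4 and the end of section 4.2.4 both bar investigators from applying further exclusions. Section 5.5.5.2 requires that the inclusion and exclusion criteria still be met before a new treatment course after relapse.

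**The concern.** The synopsis sentence is a condition for entry: a patient may come in only without pitting edema. Criterion 15 moves that wording into a list of reasons to keep patients out but leaves the negation in place. The meaning is then reversed, and being free of pitting edema becomes part of what disqualifies.

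Swelling is a known effect of this drug, so a screening rule about edema should have one clear meaning. A site that follows Section 4 to the letter has no basis in criterion 15 for turning away a patient because of pitting edema, and it may not add one of its own.

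**Working it through.** No figure in the plan depends on this wording, so the check is a comparison of texts followed by a count of who could be affected.

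**1. What each text excludes.** Let S be skin signs suggesting edema and P be pitting edema.

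| Patient has | Synopsis | Criterion 15, read as one joined condition | Criterion 15, read with the opening words governing |
|---|---|---|---|
| S, no P | excluded | excluded | excluded |
| S and P | excluded | not excluded | excluded |
| P, no S | excluded | not excluded | not excluded |
| neither | eligible | eligible | eligible |

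- The synopsis excludes S or P, which is 3 combinations.
- If the closing words of criterion 15 are read as a joined condition (S and not P), it excludes 1 of those 3.
- If the opening reference to lymphedema is taken to decide the matter and the rest is treated as elaboration, it excludes 2 of the 3.
- On neither reading is pitting edema a reason for exclusion in itself. To obtain the synopsis rule, the reader must import the synopsis sentence.

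**2. Which text a site should follow.** The synopsis points to Section 4. Section 4 also says that deviation from any entry criterion excludes a patient, and section 11 permits no authorized deviations. The faulty text is therefore the operative one.

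**3. How many patients it can touch.**

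- First-course enrolment: Section 4 plans approximately 19 patients in Part C, and the exposure summary in the Introduction gives 18 already exposed. 19 − 18 = about 1, plus any replacements. It may be none, because enrolment beyond about 15 was optional.
- Re-dosing check: the ceiling is 11 (Part B) + 18 (Part C) = 29 patients. The real number is well below this. Section 5.5.5.2 also asks for six doses, good tolerability, no early discontinuation, more than 50% volume reduction, symptomatic relapse with regrowth, and at least 6 months since the last dose.
- The documents do not say how many of these patients have pitting edema.

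**4. The clinical background.** Section 3.5.1 reports periorbital swelling in "1 of 5 patients in Part A, in 6 of 11 MCS110 treated patients in part B and in 15/18 patients" in Part C. The sum is (1 + 6 + 15) / (5 + 11 + 18) = 22/34 = 64.7%. The same section says that every case was mild and needed no treatment.

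**The case against.** The best defense is that nobody would be misled. The synopsis states the rule correctly in the same document. Criterion 15 lists swelling among its signs, and pitting edema will often show as swelling, so the group with pitting but no other sign is probably small. Much of this stands, and it is why the point is minor. It does not make the criterion correct: no reading of the clause excludes pitting edema as the synopsis does.

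Swelling that appears on treatment is also handled elsewhere. In Parts B and C, section 5.5.5.2 says that dosing after periorbital swelling "will be put on hold until one week after the swelling has resolved", and section 3.5.5 adds "Patients will only be re-dosed once the AE resolved". These rules limit the consequence of the error. They act after exposure, however, and do not supply the missing entry rule.

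Three stronger readings are tempting, and the documents do not support them.

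- A reader might infer that the protocol's stated protection against edema fails, because section 3.5.1 says "We will exclude patients with an increased risk in developing edema". That sentence goes on to name renal, hepatic or cardiac dysfunction as its examples. Criteria 5a, 11, 12 and 13 deal with heart failure, liver, kidney and troponin, and their wording is sound. The sentence should not be taken as a description of criterion 15.
- A reader might infer from 22 of 34 that patients with pitting edema at baseline face a serious hazard. The swelling counted there arose on treatment and was mild, and nothing in the documents links it to pitting edema at entry.
- A reader might infer a matching error for lung disease, since section 3.5.1 describes that exclusion more broadly than the list does. That section is a risk narrative and may be shorthand. The documents do not show which text is right, so this is not an established error.

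**Conclusion.** Criterion 15 is wrong as written, and the point is minor. The conclusion rests on the wording alone: each listed item is a reason to exclude, the clause places absence of pitting edema inside that reason, and the synopsis says the reverse while deferring to Section 4.

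The practical reach is about 1 remaining planned enrolment (possibly none) plus replacements, and a re-dosing group well under its ceiling of 29. These counts assume that the planned total of approximately 19 and the 18 exposed refer to the same set of Part C patients.

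The documents show no wrongly enrolled patient. No endpoint, analysis or sample size figure changes.

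**What to change.** At the end of criterion 15, replace *and no* with *or any* before *pitting edema*, with a comma ahead of it. The closing words then run: suggesting edema, or any pitting edema at any site, followed by the existing list of body areas. Apply the corrected criterion to any remaining enrolment, including replacements, and to the eligibility check before re-dosing.

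The cost is one clause. Section 11.1 requires a written amendment for any change, so the correction can go in with the next one. It brings Section 4 into line with the synopsis and asks for no new assessment, because section 6.5.1 already has the physical examination look for edema.
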